4.3.1 Visits

Visits will be performed at the baseline and every 4 hours for the first 24 hours, every 6 hours for day 2 and day 3.

At each visit we will record:

- An Arterial Blood Gases (ABG) sample will be collected and ABG parameters recorded (pH, PaCO₂, PaO₂, HCO₃⁻, Lactates, SaO₂);
- Glasgow Coma Scale, RASS (see APPENDIX 1-2), the dosage of remifentanil and TTS-fentanyl;
- Respiratory parameters: Ventilation mode, Pressure Support, Respiratory Rate (RR), Tidal Volume(V_t), peep, FiO₂, EtCO₂, SpO₂; if patient is spontaneously breathing: FiO₂, RR, SpO₂.
- Hemodynamic parameters (Heart Rate, SBP/DBP/MAP, need for vasopressors, inotropes).

A baseline 1-hour recording of EAdi, flow, and Paw waveforms will be performed, as well as after 1, 6, 12, 24 for the first day from the time of randomization and every 24 hours for the following days until the end of the observation period for the primary endpoint. Each recording will last one hour for patients mechanically ventilated, 10 minutes for patients weaned from the mechanical ventilator.

Four different situations are possible:

- For patients connected to the mechanical ventilator in pressure support ventilation (PSV), we will perform an expiratory pause maneuver and an inspiratory pause maneuver (both lasting enough to have 2 or 3 spontaneous breaths) with an interval of one minute between each maneuver. The maneuvers will be performed after 30 and 60 minutes from the start of recording.
- If in the meantime the patient is weaned from the mechanical ventilator and spontaneously breathing through a tracheostomy, we will temporarily reconnect the patient to the mechanical ventilator, in PSV mode, with zero peep (ZEEP), we will perform an expiratory

pause maneuver and an inspiratory pause maneuver (both lasting enough to have 2 or 3 spontaneous breaths) with an interval of one minute between each maneuver. In these weaned patients, the maneuvers will be performed after 5 and 10 minutes from the start of recording that will last only 10 minutes;

- If in the meantime the patient is weaned from the mechanical ventilator, extubated, spontaneously breathing and able to cooperate, the patient will be asked to inspire in a close system connected to a pneumotachograph to estimate P_{aw} . The maneuver will be performed after 5 and 10 minutes from the start of recording that will last only 10 minutes;
- If in the meantime, the patient is weaned from the mechanical ventilator, extubated, spontaneously breathing, and unable to cooperate we will use as a surrogate the neuromechanical efficiency calculated when the patient was connected to the ventilator. The recording will last only 10 minutes.

We will calculate $PEI_{occl,paw}$, the $Pmus_{EAdi}$ waveform, and the two most validated indexes of inspiratory effort: $\Delta Pmus$ and the PTP_{EAdi} (a good indicator of the metabolic work of breathing). We will analyze the dynamic transpulmonary driving pressure, corresponding to the sum of the pressure support level and $Pmus_{dyn}$, and representing a surrogate of dynamic stress that takes into account the chest wall elastance. Moreover we will measure the plateau pressure, the positive end-expiratory pressure (PEEP), and we will calculate the driving pressure and the static compliance of the respiratory system.

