4.1 Screening Period

The subject will be evaluated for eligibility for the study based on the inclusion and exclusion criteria. A pregnancy test for females in fertile age and an informed consent will be obtained from the subject or proxy, and/or a third party and signed by the investigator, prior to performing any assessment that is considered to be specifically mandated by the study.

Patients considered eligible for the study will be randomized in two arms. An EAdi Catheter, which is a standard nasogastric tube for enteral nutrition, will be positioned and connected to a mechanical ventilator provided with an EAdi module (Servo-U ventilator, Maquet). EAdi, flow, and Paw waveforms will be acquired from the Servo-U ventilator via a RS232 serial port connected to a laptop with dedicated software (SERVO Tracker SCI, version 1.0, Maquet Critical Care 2017). Baseline data will be collected before randomization.

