- Respiratory parameters: Ventilation mode, Pressure Support, Respiratory Rate, Tidal Volume, peep, FiO_2 , EtCO_2 , SpO_2 ; if spontaneously breathing: FiO_2 , RR, SpO_2
- Haemodynamic parameters

4 Hours

Day 1
Visits every 4 hours

- If $\text{PaCO}_2 > 45 \text{ mmHg}$ $\downarrow 0.025 \text{ mcg/kg/min}$
- If $\text{PaCO}_2 40-45 \text{ mmHg}$ $\downarrow 0.0125 \text{ mcg/kg/min}$
- If $\text{PaCO}_2 35-40 \text{ mmHg}$ \approx no changes
- If $\text{PaCO}_2 30-35 \text{ mmHg}$ $\uparrow 0.0125 \text{ mcg/kg/min}$
- If $\text{PaCO}_2 < 30 \text{ mmHg}$ $\uparrow 0.025 \text{ mcg/kg/min}$

Day 2 and 3
Visits every 6 hours

- If $\text{PaCO}_2 > 45 \text{ mmHg}$ $\downarrow 0.025 \text{ mcg/kg/min}$
- If $\text{PaCO}_2 30-45 \text{ mmHg}$ $\downarrow 0.0125 \text{ mcg/kg/min}$
- If $\text{PaCO}_2 < 30 \text{ mmHg}$ $\uparrow 0.0125 \text{ mcg/kg/min}$

EAdi, flow and Paw waveforms will be recorded 1, 6, 12, 24 hours from the time of randomization for day 1 and every 24 hours for the following days.

Figure 3. Treatment Period Group 2

[figure not shown]

Figure 4. Study Design

Screening Period	Verify inclusion/exclusion Criteria, Obtain Pregnancy test and Informed consent
Patient Enrolled	Baseline: ABG sample, respiratory and hemodynamic parameters, GCS, RASS, dosage of remifentanil at inclusion, 1-hour recording of EAdi, flow, and Paw
Treatment period	Randomization (group 1 remifentanil alone, group 2 remifentanil + TTS-fentanyl)
1 hour*	Recording of EAdi, flow, and Paw
4 hours* (Visit 1)	ABG sample, respiratory and hemodynamic parameters, GCS, RASS, dosage of remifentanil and TTS-fentanyl
6 hours*	Recording of EAdi, flow, and Paw
8 hours* (visit 2)	ABG sample, respiratory and hemodynamic parameters, GCS, RASS, dosage of remifentanil and TTS-fentanyl
12 hours* (visit 3)	ABG sample, respiratory and hemodynamic parameters, GCS, RASS, dosage of remifentanil and TTS-fentanyl, Recording of EAdi, flow, and Paw

16 hours* (visit 4)	ABG sample, respiratory and hemodynamic parameters, GCS, RASS, dosage of remifentanil and TTS-fentanyl
20 hours* (visit 5)	ABG sample, respiratory and hemodynamic parameters, GCS, RASS, dosage of remifentanil and TTS-fentanyl
24 hours* (visit 6)	ABG sample, respiratory and hemodynamic parameters, GCS, RASS, dosage of remifentanil and TTS-fentanyl, Recording of EAdi, flow, and Paw
30 hours* (visit 7)	ABG sample, respiratory and hemodynamic parameters, GCS, RASS, dosage of remifentanil and TTS-fentanyl

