Analysis of the primary efficacy criterion (AUC of the work of breathing) and other quantitative variables will be assessed with the Wilcoxon-Mann-Whitney sum of rank test. Categorical outcomes will be compared with the chi-square test, or Fisher's exact test, as appropriate: Cochran-Mantel-Haenszel statistics will be reported for all these results. Two-way analysis of variance (ANOVA) for repeated measures with Bonferroni correction will be used to determine the differences in work of breathing per breath, inspiratory effort, delta EAdi, plateau pressure, P 0.1 respiratory rate, tidal volume, arterial blood pressure, heart rate in the two groups. Comparisons between groups regarding these variables at each study time point will be performed with the Student's t-test or Mann-Whitney test, as appropriate. Mean difference and 95% confidence interval [CI95%] are reported for most significant results.

Two-tail p values≤0.05 Will be considered significant. Statistical analysis will be performed with SPSS software package (SPSS Inc. Released 2009. PASW Statistics for Windows, Version 18.0. Chicago: SPSS Inc.).

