6.1 Sample size calculation

As said previously, the primary endpoint is to demonstrate that the area under the curve (AUC) of the work of breathing per minute (assessed at 1, 6, 12, 24, 48, and 72 hours) in the intervention group is not higher than the control group. Data on the work of breathing of ICU patients undergoing mechanical ventilation while on remifentanil continuous infusion are lacking. However, there are studies suggesting that a sample of 10 patients is adequate to draw significant conclusions on the physiological endpoints related to respiratory mechanics and work of breathing among patients with respiratory failure (Delorme et al. 2017; Lellouche et al. 2002; Prat et al. 2003; LHer et al. 2005). Thus, for this phase II, pilot, randomized trial, using a conservative approach and considering an attrition rate lower than 10%, we planned to enroll 12 patients per group, for a total sample of 24 patients in 12 months. Julius et al., in their study published on pharmaceutical statistics in 2005 confirmed that a minimum 12 subjects per group are enough for a pilot randomized trial (Julious et al. 2005).

7. Premature withdrawal from the study

Subjects may voluntarily withdraw from the study without justification for any reason at any time. Subjects are considered withdrawn if they state an intention to withdraw further participation in all components of the study (i.e., withdrawal of consent), die within the observation period for the primary endpoint, or are lost to follow up. If a subject withdraws consent, no further data will be collected in the CRF from the date of withdrawal onward. The investigator may withdraw a subject from the study (without regard to the subject's consent) if he/she believes that continued participation in the study would be contrary to the best interests of the subject.

The reason for premature withdrawal from the study must be recorded in the CRF.

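### The primary work-of-breathing AUC is compared without adjustment, although the same signals are recorded for one hour before randomisation

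*Combined protocol and SAP*

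**What the plan says.** Section 2.2 defines the primary endpoint as the AUC of work of breathing per minute from recordings made after randomisation. Section 6.1 lists the times: "assessed at 1, 6, 12, 24, 48, and 72 hours". Time zero is not among them.

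Section 6 gives the primary method: "Analysis of the primary efficacy criterion (AUC of the work of breathing) and other quantitative variables will be assessed with the Wilcoxon-Mann-Whitney" test. It names no covariate, change from baseline or strata. The repeated-measures ANOVA in the same section is assigned to other variables, such as work of breathing per breath. Whether baseline is one of its levels is not stated. The Cochran-Mantel-Haenszel statistics are attached to the categorical outcomes.

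The same signals are recorded at baseline. Section 4.3.1: "A baseline 1-hour recording of EAdi, flow, and Paw waveforms will be performed". Section 4.1: "Baseline data will be collected before randomization". Table 1 lists "dosage of remifentanil at inclusion, 1-hour recording of EAdi, flow, and Paw" in the row above randomisation. According to the Abstract, every patient receives the catheter.

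**The concern.** The plan collects what is often a useful predictor of the primary outcome, namely the outcome's own pre-treatment value, and then leaves it out of the primary comparison. Two things follow if baseline and later effort are correlated.

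- **Precision.** The objective is non-inferiority (Section 2.1), so the conclusion rests on a confidence limit for the difference. Between-patient variation that baseline could explain stays in that limit and widens it.
- **Chance imbalance.** With 12 patients per arm from three ICUs and no stratification described, the arms can easily differ at baseline. A baseline difference passes into the AUC difference in proportion to r. If the fentanyl arm happens to start lower, the unadjusted comparison favours it, and the planned test cannot remove this.

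**Working it through.** **Inputs from the documents.** 12 per arm, 24 in total; attrition below 10% (Section 6.1); two-sided 5% level (Section 6). The documents give no SD, effect size, power, margin or r. Results are therefore in SD units of the AUC on the analysis scale, and r is assumed over 0 to 0.7.

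**The plan's own figure.** A precedent of 10 patients, read as per group, inflated for 10% attrition gives 10/(1 − 0.10) = 11.1, rounded up to 12. This reproduces the stated size but checks only the attrition arithmetic.

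**Chance imbalance.** The difference in baseline means has SD √(2/12) = 0.41, so P(|difference| > 0.5 SD) = 22%. With 11 per arm it is 24%.

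**Effect of adjustment.** With N = 24, ANCOVA multiplies the variance of the treatment difference by (1 − r²)(N − 3)/(N − 4) = (1 − r²) × 1.05. Break-even is r = √(1 − 1/1.05) = 0.22. Example at r = 0.4:

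- factor 0.84 × 1.05 = 0.882
- ANCOVA half-width 2.080 × √(2/12 × 0.882) = 0.80 SD
- unadjusted half-width 2.074 × √(2/12) = 0.85 SD

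Simulated mean half-widths are about 0.01 SD smaller, because the sample SD averages slightly below the true SD. The simulation used 40,000 replicates of bivariate normal data. The 1 SD difference is a yardstick only.

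| r | 0 | 0.2 | 0.3 | 0.4 | 0.6 | 0.7 |
|---|---|---|---|---|---|---|
| 95% CI half-width, ANCOVA, 12 per arm (unadjusted 0.84) | 0.86 | 0.84 | 0.82 | 0.79 | 0.69 | 0.61 |
| Same, 11 per arm (unadjusted 0.88) | 0.90 | 0.89 | 0.86 | 0.83 | 0.72 | 0.65 |
| Power at 1 SD, ANCOVA, % | 63 | 64 | 67 | 70 | 82 | 89 |
| Power at 1 SD, rank-ANCOVA, % | 61 | 62 | 64 | 67 | 77 | 84 |
| Shift in unadjusted AUC difference from a 0.5 SD imbalance (0.5 × r) | 0 | 0.10 | 0.15 | 0.20 | 0.30 | 0.35 |

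Unadjusted power is 61% for Wilcoxon and 65% for a t-test. About 4 points of ANCOVA's gain over Wilcoxon therefore come from leaving ranks, not from adjustment.

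**Error rates with no treatment effect.** Overall type I error is about 4.5% for Wilcoxon and 5% for ANCOVA and rank-ANCOVA. If the imbalance is exactly 0.5 SD, the chance that Wilcoxon declares the higher-baseline arm worse rises from 2.2% at r = 0 to 4.6% at r = 0.4 and about 5.5% at r = 0.6 to 0.7. Errors in the other direction shrink, so the two-sided total moves only from about 4.5% to 5.5%. Across all null trials with an imbalance above 0.5 SD, Wilcoxon's two-sided error is about 6% at r = 0.3, 8 to 10% at r = 0.5 and 13 to 14% at r = 0.7. ANCOVA stays near 5%.

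**Scale.** On assumed lognormal data (log-SD 1), ANCOVA on unlogged values has 47% power at r = 0.4, below the planned Wilcoxon test's 61%.

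**The case against.** The best defence is that an unadjusted rank test is a legitimate choice for a 24-patient pilot: it is valid, and it contradicts no power or margin in the plan. The benefit depends on an r that the documents do not give. Comparing rank methods like for like, the power gain is 0, 1, 3 and 6 points at r = 0, 0.2, 0.3 and 0.4; large gains need r of 0.6 or more. All of this stands. It makes the point one of efficiency and robustness, not validity.

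There are also reasons in the documents why r could be low. Both arms are titrated to PaCO₂ throughout, which may weaken the dependence on baseline. Later recordings can be short: "Each recording will last one hour for patients mechanically ventilated, 10 minutes for patients weaned from the mechanical ventilator". For extubated patients who cannot cooperate, "we will use as a surrogate the neuromechanical efficiency calculated when the patient was connected to the ventilator". That last provision could equally raise r, because it carries an earlier factor into later values. None of this fixes r, which is why the range starts at zero. The loss at r = 0 is small (0.86 against 0.84 SD).

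The timing of baseline could be questioned too. Section 4.1 mentions randomisation before it describes catheter placement, and Section 4.2 starts the treatment period with the baseline assessments. The explicit sentence in Section 4.1 and the order of Table 1 settle the reading as pre-randomisation, but the wording should be made consistent.

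**Conclusion.** The concern holds. A pre-randomisation recording of the primary signals is scheduled for every patient, and the primary comparison ignores it. The planned test is not invalid. The cost is a wider interval than necessary when r exceeds about 0.22, and no correction when the arms start unequal, which exceeds 0.5 SD in 22% of trials of this size. At r = 0.4 the half-width would fall from 0.84 to 0.79 SD; at r = 0.7 it would fall to 0.61 SD. These sizes assume normality on the analysis scale and an r that the documents do not supply. No margin is stated, so the gain cannot be turned into non-inferiority power.

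**What to change.** Before any data are seen, pre-specify one primary model: ANCOVA of log AUC (1 to 72 h) on arm, with log baseline work of breathing per minute as the single covariate. Report the adjusted ratio of geometric means with its 95% CI. If a rank method is to stay primary, specify rank-ANCOVA (AUC rank on baseline rank) instead. Do not fit ANCOVA to unlogged skewed data. Keep the unadjusted Wilcoxon test as a sensitivity analysis.

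In the same edit:

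- state how work of breathing per minute is computed from the recordings, since Section 4.3.1 lists effort indices but no formula for it;
- state how a failed baseline recording is handled, since it would drop the patient from the model;
- align Sections 4.1 and 4.2 with Table 1 so that the covariate is plainly pre-randomisation.

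The cost is SAP wording and one degree of freedom, with no new measurements. The risk is a slight loss of precision if r is below about 0.22.

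### With visibly different arms, the plan provides no masked waveform reading and no rule for the occluded breaths, leaving a Pmus-based primary endpoint open to detection bias

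*Combined protocol and SAP*

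**What the plan says.** - **Arms.** Sections 3.1 and 4.2 describe two arms that anyone at the bedside can tell apart: patches plus remifentanil, or remifentanil alone. No placebo patch is described. The design, visit, statistical and data-handling sections mention no masking of patients, staff, waveform readers or analysts.
- **Endpoint.** Sections 2.2 and 6.1 define the primary endpoint as the AUC of work of breathing per minute at 1, 6, 12, 24, 48 and 72 hours. Under Section 6 it "will be assessed with the Wilcoxon-Mann-Whitney sum of rank test", and "Two-tail p values≤0.05 Will be considered significant".
- **Acquisition.** EAdi, flow and airway pressure come from the ventilator, which is "connected to a laptop with dedicated software" (Section 4.1).
- **Occlusions.** In patients on pressure support, and in those reconnected through a tracheostomy, Section 4.3.1 asks for an expiratory and an inspiratory pause, "both lasting enough to have 2 or 3 spontaneous breaths", at two times in each recording.
- **Derivation.** Section 4.3.1 then has PEI, the Pmus waveform and "the two most validated indexes of inspiratory effort" calculated, the latter being ΔPmus and the pressure-time product (PTP). Section 1.4 gives Pmus = EAdi × PEI.
- **What is absent.** No text says who reads the traces, which occluded breaths count, whether they are averaged, or how Pmus or PTP becomes work of breathing per minute.
- **Identification.** Section 10 has subjects identified by number only on the CRF and other documents, and the investigator keeps the list linking numbers to people.

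**The concern.** PEI is a scale factor derived from a handful of occluded breaths. Where the rule for choosing or averaging those breaths is open, and the person applying it can know the arm, small judgments can lean the same way throughout one arm. Number-only identification protects the patient's identity; it does not hide allocation.

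The aim is to show that work of breathing is not higher with the patch. A lean toward lower readings in the patch arm would therefore favor the hypothesis and could hide a true increase. With 12 patients per arm, a modest systematic shift is hard to tell from a treatment effect.

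**Working it through.** **1. The plan's own sample size.** Section 6.1 starts from the view that "a sample of 10 patients is adequate to draw significant conclusions on the physiological endpoints", adds an allowance "considering an attrition rate lower than 10" percent, and concludes that "we planned to enroll 12 patients per group, for a total sample of 24 patients in 12 months".

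10 / (1 − 0.10) = 11.1, rounded up to 12 per arm, 24 in total. The figure reproduces. The plan gives no effect size, SD, power or non-inferiority margin, so this confirms the arithmetic only. Masked reading does not change it.

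**2. How many readings feed the endpoint.** 24 patients × 6 post-randomization recordings = 144 recordings; × 2 maneuver times = 288. This is an upper bound, because Section 4.3.1 distinguishes four situations:

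| Situation | Maneuver | 2–3 breath pauses? |
|---|---|---|
| Pressure support | at 30 and 60 min | yes |
| Weaned, tracheostomy, reconnected | at 5 and 10 min | yes |
| Extubated, cooperative | inspiration in a closed system at 5 and 10 min | no breath count given |
| Extubated, not cooperative | none; a PEI from the ventilated period is reused | no |

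**3. How an error in PEI reaches the AUC.** Trapezoid weights over 1–72 h are 2.5, 5.5, 9, 18, 24 and 12 (sum 71). If PEI is read as (1 + b) × PEI at every recording, each Pmus value is multiplied by (1 + b). Provided work of breathing per minute is proportional to Pmus, so is the weighted sum: AUC becomes (1 + b) × AUC. An error at one recording counts by its weight; if work is level over time, an error at 48 h alone shifts the AUC by 24/71 = 34% of b.

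The factor of 1.25 mentioned in Section 1.4 is missing from the equation there, and Section 4.3.1 does not say whether it is applied. Applied to every value alike, it would not alter ranks and so is not itself a source of arm bias.

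**4. How large b could be.** The documents give no within-session variability. Two expiratory pauses of 2 or 3 breaths give 4 to 6 candidate breaths. For normally distributed readings, the expected extreme lies 1.03 (of 4) to 1.27 (of 6) SDs from the mean. Always taking the lowest or highest breath instead of the mean would move PEI by:

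- 5–6% at an assumed within-session CV of 5%;
- 10–13% at 10%;
- 21–25% at 20%.

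This is a limiting case. It creates a difference between arms only if done in one arm and not the other.

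**5. What a shift does to the primary test.** Simulation: 12 per arm, log-normal AUC, two-sided Wilcoxon-Mann-Whitney at 0.05, 20,000 runs. All between-patient CVs and shifts are assumptions.

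| Downward shift in patch arm | False finding of lower work, CV 30% | Same, CV 60% | Detects a true 25% increase, CV 30% | Same, CV 50% |
|---|---|---|---|---|
| 0% | 2.2% | 2.1% | 39.2% | 17.5% |
| 5% | 5.1% | 3.4% | 24.9% | 11.6% |
| 10% | 11.6% | 5.8% | 13.5% | 7.4% |
| 15% | 23.2% | 9.0% | 6.2% | 4.3% |

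The second and third columns assume no true difference between arms.

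**The case against.** The strongest reply is that the signals are machine-recorded and the plan is merely silent. Much of that stands, and it rules out several stronger readings.

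- **A reader might infer that breaths are hand-picked offline and that the recordings are uncoded.** The documents say neither. Averaging every occluded breath fits the text equally well, and coded files are neither required nor ruled out.
- **A reader might infer that every work-of-breathing value is exposed.** That needs work of breathing per minute to be computed from Pmus. Section 4.3.1 implies this, but no formula states it. The open choice among 2–3 breaths also does not arise for extubated patients.
- **A reader might count seven recordings per patient (168 recordings, 336 maneuver times).** The seventh is the baseline, which is taken before randomization and is not among the AUC time points in Section 6.1.
- **A reader might conclude that such bias could never be checked.** The waveforms are acquired digitally, so retained recordings could be re-read by someone masked. ΔEAdi, which does not use PEI, is also analyzed (Sections 2.2 and 6) and offers a partial cross-check.

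What the reply does not meet is this: PEI still has to be derived from occluded breaths under some rule, the plan states none, and nothing keeps the person deriving it from knowing the arm.

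**Conclusion.** The point holds as a gap in protection, not as evidence that readings are or will be biased. Arms are visibly different, no masked reading is provided for, and the acceptance and averaging of occluded breaths is left open for patients on pressure support or reconnected through a tracheostomy. Any proportional arm-related difference in PEI passes one-for-one into a Pmus-based AUC, across at most 144 recordings and 288 maneuver times.

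The size of such a difference is unknown. A range of 5–15% is an assumption for illustration, and the documents support no estimate. If it were 10% downward in the patch arm, false findings of lower work would rise from about 2% to 6–12% (assumed between-patient CV 60% down to 30%), and a true 25% increase would be detected less often. These figures rest on assumed CVs, a log-normal AUC and work of breathing proportional to Pmus. It is a modest weakness with an inexpensive remedy.

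**What to change.** Add a paragraph to Section 4.3.1 providing that:

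1. Before analysis, the stored recordings are exported under a random study code that hides arm, drug dose and trial patient number. The code keeps a within-patient link and time order; otherwise the PEI reuse prescribed for uncooperative extubated patients could not be done while masked.
2. An existing team member other than the person reading the traces holds the key.
3. The existing analyst computes PEI, Pmus, PTP and work of breathing per minute from the coded files under one fixed rule, for example the mean of all accepted occluded breaths. The rule states the acceptance criteria, the formula for work of breathing per minute, whether the 1.25 factor applies, and which earlier PEI is reused.
4. The AUC dataset is locked before arm is linked.

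**Cost.** File recoding, a key-holding task for existing staff, one paragraph of text and a short delay before results by arm are available. There is no additional reader, no change to patient procedures, and the sample size stays at 24. Staff performing the maneuvers will still know the arm, so the change reduces the risk of bias without removing it.
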